4.3.2 End of study

The study will end when the last patient completes treatment, or 30 days after the last patient discontinues from the study, or early termination of the study, whichever comes first.

The Clinical Study Report (CSR) will be written at the end of the trial when all patients have discontinued.

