6.1.5 Treatment duration

The planned duration of treatment is at least 2 years. Patients may be discontinued from treatment with the study drugs due to documented disease progression, intolerable toxicity, withdrawal of consent, discontinuation at the discretion of the investigator, or lost to follow-up, whichever comes first. Patients who complete 2 years of treatment and are deriving clinical benefit in the opinion of the investigator will be allowed to continue receiving treatment (LDE225 and INC424) in an extension phase of this study, until discontinuation reasons are met or an alternative setting to receive study treatment (e.g., in form of another protocol) becomes available.

The extension phase will begin on the day after the Week 105 visit. The first extension phase visit will occur 12 weeks after the Week 105 visit. See [Table 7-2](#) for the schedule of assessments during the study extension phase.

A safety follow-up will be conducted 30 days (+3 days) after the last dose of study medication is received and a study completion form will be completed in the eCRF. The safety follow-up

may be waived if the patient is continuing on INC424 and LDE225 treatment in an alternative setting.

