7.2.1.2 Measurement of spleen volume by MRI/CT

Patients enrolled to the confirmatory MTD level(s) in the Phase Ib part and all patients enrolled in the Phase II part of the study will have MRI/CT of the abdomen performed at Week 1 Day 1, Week 13 Day 1, the end of Week 24, the end of Week 48, and at Week 105 Day 1. Patients in the extension phase will undergo MRI/CT of the abdomen every 24 weeks from Week 105. All patients will undergo MRI/CT of the abdomen at the End of Treatment visit. Patients who have a $\geq 35\%$ spleen volume reduction at the end of Week 24 and Week 48 compared to Week 1 Day 1 will be considered responders, otherwise they will be considered non-responders. See [Table 7-3](#) for the imaging collection plan.

Table 7-3 Spleen volumetric imaging (MRI/CT) collection plan

| Procedure | Collection time points |
|--|--|
| Abdominal MRI of the spleen (or CT if MRI not permitted) Phase Ib- Patients enrolled to the confirmatory MTD level(s) Phase II- All Patients | Week 1 Day 1 |
| | Week 13 Day 1 |
| | At the end of Week 24 and the end of Week 48, and Week 105 Day 1 |
| | Every 24 weeks from Week 105 for patients in the extension phase |
| | End of Treatment |
| Central Reader: MRI/CT scans will be sent to a central lab for analysis | |

MRIs will be performed locally according to the guidelines provided by the designated imaging vendor. The scans from an individual patient will be sent to the designated imaging vendor, who will then provide an independent quantitative assessment of the spleen volume for the study. Spleen volume will be obtained by outlining the circumference of the organ and determining the volume using a validated technique. The MRI will not determine spleen length below the left costal margin, as there are no validated approaches for determining this

measurement. Specific image acquisition parameters and procedures will be provided by the designated imaging vendor.

MRI is the preferred method for obtaining spleen volume data. However, CT scans may be performed if MRI cannot be performed (because of the presence of metal clips in the body, or because of claustrophobia, for example), or if MRI is unavailable to the study site. CT scans will be similarly processed by the designated imaging vendor.

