7.2.1.3 Change in bone marrow histomorphology

Bone marrow fibrosis will be measured in grades (see [Table 7-4](#)) on biopsy samples obtained for all patients at Week 1 Day 1, Week 25 Day 1, Week 49 Day 1, Week 73 Day 1, and Week 97 Day 1. For patients in the extension phase, biopsy samples will be obtained every 48 weeks from Week 105. Biopsy samples will also be obtained at the End of Treatment visit, if a sample has not already been obtained in the past 24 weeks (see [Table 7-5](#)). Collection, processing and staining of bone marrow aspirations and biopsy samples will be done in accordance with standard procedures at the investigative sites. The bone marrow biopsy and aspirate should be assessed by an experienced hematopathologist using his/her standard examination. Bone marrow fibrosis should be graded using the European consensus grading system ([Tefferi 2006](#)).

[figure not shown]
Table 7-4 Fibrosis grading

| Fibrosis Grade | Description |
|----------------|--|
| 0 | Scattered linear reticulin with no intersections corresponding to normal bone marrow |
| 1 | Loose network of reticulin with many intersections, especially in perivascular areas |
| 2 | Diffuse and dense increase in reticulin with extensive intersections, occasionally with only focal bundles of collagen and/or focal osteosclerosis |
| 3 | Diffuse and dense increase in reticulin with extensive intersections with coarse bundles of collagen, often associated with significant osteosclerosis |

Note: Fibrosis density should be assessed in hematopoietic areas.

The following analyses should be performed:

- Assessment of cellularity.
- 500-cell differential of aspirate, correlated, if possible, with data from appropriate marrow biopsy section. Percentage of pronormoblasts, blasts, normoblasts, myelocytes, metamyelocytes
- Blast percentage, indicating what cellular types are being considered as blast equivalents, and the degree of maturation and dysplastic abnormalities within the neoplastic population should be described.
- Characterization of erythrocyte and megakaryocyte morphology.
- Characterization and gradation of fibrosis within hematopoietic cellular areas.
- Diagnostic interpretation with specific mention of (expected) absence of an infiltrative or granulomatous process

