9.4 Database management and quality control

Novartis personnel (or designated CRO) will review the data entered by investigational staff for completeness and accuracy. Electronic data queries stating the nature of the problem and requesting clarification will be created for discrepancies and missing values and sent to the investigational site via the EDC system. Designated investigator site staff are required to respond promptly to queries and to make any necessary changes to the data.

Concomitant treatments and prior medications entered into the database will be coded using the WHO Drug Reference List, which employs the Anatomical Therapeutic Chemical classification system. Medical history/current medical conditions and adverse events will be coded using the Medical dictionary for regulatory activities (MedDRA) terminology.

ECGs will be read locally. Samples and/or data for imaging, PK, Biomarker (blood and derivative), and bone marrow biopsies/aspirates will be processed centrally and the results will be sent electronically to Novartis (or a designated CRO).

After database lock, the investigator will receive a CD-ROM or paper copies of the patient data for archiving at the investigational site.

10 Statistical methods and data analysis

Data from this trial will be analyzed by Novartis and/or a designated CRO. All data analysis carried out independently by the investigator should be submitted to Novartis before publication or presentation.

All data from participating centers in this protocol will be combined so that an adequate number of patients will be available for analysis. The data related to demographic and baseline characteristics, efficacy observations and measurements, safety observations and measurements, and all relevant PK and PD measurements will be summarized using descriptive statistics (quantitative data) and contingency tables (qualitative data).

The final analysis of study data for the purposes of generating the Clinical Study Report (CSR) will be based on all patient data from phase I (including dose escalation and safety expansion phases), phase II, and the extension phase, when all patients have discontinued the study.

Details of the statistical analysis and data reporting will be provided in the Novartis Report and Analysis Plan (RAP) document finalized before database lock.

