CDR&R	Clinical Data Review & Reporting
CRF	Case Report Form
CSP	Clinical Study Protocol
CT	Computer Tomography
CTCAE/CTC	Common Terminology Criteria for Adverse Events
CTD	Common Technical Document
DDS	Dose-determining Set
DI	Actual Dose Intensity
DLT	Dose Limiting Toxicity
ECG	Electrocardiogram
EOS	End Of Study
FAS	Full Analysis Set
GCP	Good Clinical Practice
IA	Interim Analysis
IQR	InterQuartile Range
IRT	Interactive Response Technology
ITT	Intention To Treat
JAK2	Janus kinase 2
LLOQ	Lower Limit of Quantification
MedDRA	Medical Dictionary for Regulatory Activities
MF	Myelofibrosis
MRI	Magnetic Resonance Imaging
ms	Millisecond
NCDS	Novartis Clinical Data Standards
NCI	National Cancer Institute
PAS	Pharmacokinetic Analysis Set
PDI	Planned Dose Intensity
PK	Pharmacokinetics
PPS	Per Protocol Set
PRO	Patient Reported Outcomes
RDI	Relative Dose Intensity
RAP	Report and Analysis Plan
RT-PCR	Reverse Transcription-Polymerase Chain Reaction
SAE	Serious Adverse Event
QoL	Quality of Life

SPP	Safety Profiling Plot
SSD	Study Specification Document
UNK	Unknown
WHO	World Health Organization

1 Introduction

This document describes the detailed statistical methodology of the Report and Analysis Plan (RAP) of the study CLDE225X2116. The CLDE225X2116 is a phase Ib/II, an open-label, multi-center, dose-finding study to assess the safety and efficacy of the oral combination of Sonidegib (LDE225) and Ruxolitinib (INC424) in patients with myelofibrosis (MF) (primary myelofibrosis (PMF), post-polycythemia vera myelofibrosis (post-PV MF) or post-essential thrombocythemia myelofibrosis (post-ET MF)).

This RAP describes the primary and final analysis of the data as specified in the protocol. The primary analysis of study data will be performed when all patients (Phase Ib and Phase II) have been treated for one year or discontinued treatment. The final analysis of study data for the purposes of generating CSR will be based on all patient data from phase Ib and phase II when all patients have completed at least two years of treatment or discontinued the study.

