1.1 Study design

[figure not shown]
This study consists of an open-label, multi-center, dose-finding phase Ib including dose escalation and expansion followed by a phase II in patients with MF.

The study has 3 parts:

- (1) Screening: 21 days screening assessment period prior to receiving the first study treatment.
- (2) Treatment: it includes the dose escalation and dose expansion in phase Ib and stage 1 and stage 2 in phase II. The stage 2 enrollment in phase II depends on the result for the interim analysis (IA). The treatment period is from Day 1 for up to 2 years or until death, documented disease progression, initiation of a new MF therapy, intolerable toxicity, withdrawal of consent, discontinuation at the discretion of the investigator, lost to follow-up or premature termination of the study, whichever comes first. Based on the recommendation from SC and internal decision, there will be no enrollment to Phase II Stage 2.
- (3) Follow up: 30 days following up after the last day of treatment.

The flow chart of the study design is in [Figure 1-1](#).

Figure 1-1 Study design of CLDE225X2116

Note: Patients who complete 2 years of treatment and are deriving clinical benefit in the opinion of the investigator will be allowed to continue receiving treatment (LDE225 and INC424) in an extension phase of this study, until discontinuation reasons are met or an alternative setting to receive study treatment (e.g., in form of another protocol) becomes available.

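### The SAP runs the final CSR analysis at two years, while the protocol waits until all patients have discontinued; data after the SAP cut have no planned analysis

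*SAP*

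**What the plan says.** **SAP, section 1 (Introduction).** The final analysis, which generates the CSR, uses "all patient data from phase Ib and phase II when all patients have completed at least two years of treatment or discontinued the study". The same paragraph says: "This RAP describes the primary and final analysis of the data as specified in the protocol". A separate primary analysis is set for when all patients have been treated for one year or have stopped.

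**Protocol, section 10 (opening paragraphs).** The final analysis for the CSR uses data from phase I, "phase II, and the extension phase, when all patients have discontinued the study".

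**Protocol, section 4.3.2.** "The Clinical Study Report (CSR) will be written at the end of the trial when all patients have discontinued".

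**The extension phase.** The SAP knows of it: the note to its design figure (section 1.1) says that patients who benefit after two years "will be allowed to continue receiving treatment (LDE225 and INC424) in an extension phase of this study". Protocol 6.1.5 fixes the start: "The extension phase will begin on the day after the Week 105 visit".

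**The concern.** The two documents give different triggers and, on their wording, different data scopes for the same analysis. The protocol text is current, and the Amendment 2 summary shows that the later trigger was intended. The SAP cannot be read as predating the extension. It describes the extension, and it also records the later decision not to open Stage 2.

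At stake is follow-up of the longest-exposed patients. The protocol keeps collecting data from them after Week 105, some of it burdensome, such as marrow biopsies. If the last planned analysis comes before these patients stop, the final safety tables will lack their later events, and the disposition table will show them as still on treatment.

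**Working it through.** No power, alpha or event count is involved, so the check compares the texts and counts what falls after the cut.

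**1. Trigger and scope**

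| | SAP section 1 | Protocol sections 10 and 4.3.2 |
|---|---|---|
| Trigger | Every patient has at least two years of treatment or has discontinued | Every patient has discontinued |
| Data named | Phase Ib, phase II | Phase I, phase II, extension phase |
| Change declared | None; says it follows the protocol | Not applicable |

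The triggers coincide only if nobody is still on study treatment when the last patient reaches two years.

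**2. What the SAP does with a patient still on treatment at the cut**

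- Section 3.2.1 counts the patient as ongoing, because there is no End of Treatment page.
- Section 2.1.11.6 (scenario 1) uses the cut-off date as the last dosing date.
- Section 3.3.1 ends the patient's exposure at the cut-off date.
- No visible section plans a further analysis.

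**3. What the SAP does with extension data that exist at the cut**

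- The full analysis and safety sets (2.2.1, 2.2.2) are defined by patients and have no Week 105 limit.
- The on-treatment period (2.1.7) runs to 30 days after the last dose.
- Exposure (3.3.1) has a category of 106 weeks or more.

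These data therefore stay in.

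Some such data should exist. Amendment 1 reports 30 phase Ib patients treated by 6 August 2014. Amendment 2 reports 50 treated by 6 February 2015, made up of 30 in phase Ib and 20 in Stage 1. Stage 1 closed at 20 and Stage 2 never opened (SAP 3.5.2.1.2 and 1.1). Counting two years from first dose, the SAP trigger is met no later than about February 2015 + 2 years = February 2017. Phase Ib patients still on treatment would reach two years by about August 2014 + 2 years = August 2016, so part of their extension falls before the cut if the trigger is met after that.

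**4. What falls after the cut**

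Protocol Table 7-2 captures adverse events continuously. Hematology, chemistry, CK, palpation and the MFSAF are 12-weekly. For spleen volume, "Patients in the extension phase will undergo MRI/CT of the abdomen every 24 weeks from Week 105". For marrow, "For patients in the extension phase, biopsy samples will be obtained every 48 weeks from Week 105". Table 7-2 limits scans and marrow to phase Ib expansion patients and all phase II patients.

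Per 48 weeks on treatment after the cut, each patient has:

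- 48 / 12 = 4 laboratory, palpation and symptom visits;
- 48 / 24 = 2 MRI/CT scans, where applicable;
- 48 / 48 = 1 marrow sample, where applicable;
- all adverse events in that time and, eventually, the End of Treatment assessments and the reason for stopping.

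**5. How many patients**

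Amendment 2 reports 14 of the 50 treated patients as having discontinued: 50 − 14 = 36, and 36 / 50 = 72%. At that date nobody had completed two years. So 36 is an upper bound on those who could still be on treatment at the cut. The later figure is not in the documents.

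**6. What is unaffected**

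The primary endpoint is read at Weeks 24 and 48, the DLT window is six weeks, and the interim decision used Week 24 data. All come before the two-year cut.

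**The case against.** **The scope wording can be read generously.** The extension enrols nobody new, so data on phase Ib and phase II patients can be taken to include what they contribute after Week 105. This stands for data up to the cut, and step 3 supports it. It does not resolve the trigger: data that do not yet exist cannot be in the analysis. A reader might infer that everything collected after Week 105 goes unanalysed. The SAP's analysis sets and on-treatment rules do not support that.

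**The extension serves no visible endpoint.** Amendment 2 presents it as continued access to treatment, and the phase II endpoints with stated visits are at Weeks 24 and 48. A reader might describe long-term safety as a stated secondary objective, but the documents say only safety. That weakens the point without removing it, because protocol section 10 names extension data as part of the CSR analysis.

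**The loss may be small or nil.** Patients can leave for another setting that supplies the drugs, and the 30-day follow-up may be waived for them (protocol 6.1.5 and 7.1.5). This stands.

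**Not all of the plan is visible.** SAP sections 1.4, 1.5 and 3.7.1 are not shown, and some detail is deferred to a separate RAP module. The protocol's abbreviation list defines a CSR addendum, but no visible text schedules one. The claim is therefore limited to the visible SAP.

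**SAEs still reach the sponsor within 24 hours** (protocol 8.2.2). That covers case reporting, not the study's summary tables.

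**Conclusion.** The SAP's trigger for the final CSR analysis contradicts the protocol's, and the departure is not declared. The consequence is limited to follow-up after the SAP cut in patients then still on treatment: late adverse events, SAEs and deaths, CK and other laboratory results, later scans and marrow samples, and the final reason for stopping.

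The number of patients is unknown, between 0 and 36 of 50. The figure of 36 should not be quoted as the number who lose data. It is an on-treatment count from February 2015, well before the cut.

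No efficacy conclusion changes. The conclusion assumes that no unseen section or module plans a later analysis, and that at least one patient continues past the cut. If neither holds against it, the SAP should be corrected, because the correction is cheap and otherwise the safety record of the longest-exposed patients is incomplete.

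**What to change.** In SAP section 1, replace the final-analysis trigger and scope with the protocol's: all patients have discontinued, with phase Ib, phase II and extension data included. If a two-year report is wanted, keep it and label it as an additional cut.

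Run these outputs at study end: disposition (3.2.1), exposure (3.3), adverse events, SAEs and deaths (3.8.1), and laboratory data including CK (3.8.2).

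The spleen-volume response outputs need no re-run, since they are defined only at Weeks 24 and 48. Extension MRI/CT and marrow results should be listed or summarised descriptively, which is a small addition to the existing tables.

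If the sponsor prefers the two-year cut as final, the SAP should declare it as a change from the protocol and say where later extension data will be reported.

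The cost is one SAP sentence, a re-run of mostly existing programs, and either a later CSR or an update to the two-year report.

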1.1 Study design

[figure not shown]
This study consists of an open-label, multi-center, dose-finding phase Ib including dose escalation and expansion followed by a phase II in patients with MF.

The study has 3 parts:

- (1) Screening: 21 days screening assessment period prior to receiving the first study treatment.
- (2) Treatment: it includes the dose escalation and dose expansion in phase Ib and stage 1 and stage 2 in phase II. The stage 2 enrollment in phase II depends on the result for the interim analysis (IA). The treatment period is from Day 1 for up to 2 years or until death, documented disease progression, initiation of a new MF therapy, intolerable toxicity, withdrawal of consent, discontinuation at the discretion of the investigator, lost to follow-up or premature termination of the study, whichever comes first. Based on the recommendation from SC and internal decision, there will be no enrollment to Phase II Stage 2.
- (3) Follow up: 30 days following up after the last day of treatment.

The flow chart of the study design is in [Figure 1-1](#).

Figure 1-1 Study design of CLDE225X2116

Note: Patients who complete 2 years of treatment and are deriving clinical benefit in the opinion of the investigator will be allowed to continue receiving treatment (LDE225 and INC424) in an extension phase of this study, until discontinuation reasons are met or an alternative setting to receive study treatment (e.g., in form of another protocol) becomes available.

1.2 Primary Objectives

The primary objective of Phase Ib is to establish the MTD and/or RPIID of the combination of LDE225 (QD) and INC424 (BID) when administered orally to patients with myelofibrosis who have not previously received therapy with a JAK inhibitor.

The primary objective of Phase II is to assess the efficacy of the co-administration of LDE225 and INC424 on spleen volume reduction as determined by centrally reviewed MRI/CT.

[figure not shown]
1.3 Secondary objectives

[figure not shown]
[figure not shown]
Phase Ib:

- To evaluate the safety of the co-administration of LDE225 and INC424 in patients with MF
- To characterize the single and multiple dose pharmacokinetics following the co-administration of LDE225 and INC424

Phase II:

- To assess the effect of the co-administration of LDE225 and INC424 on bone marrow fibrosis by central review and on disease-specific pharmacodynamic biomarkers as a function of the molecular disease characterization of MF
- To evaluate the safety of the co-administration of LDE225 and INC424 in patients with MF
- To characterize pharmacokinetics following the co-administration of LDE225 and INC424
- To assess the effect of the co-administration of LDE225 and INC424 on MF-associated symptoms burden

1.6 Patient population

The patient population will consist of adult patients, aged ≥ 18 years who have been diagnosed with PMF, post-PV MF, or post-ET MF without previous treatment with JAK inhibitor, meet intermediate or high risk prognostic criteria and exhibit palpable splenomegaly ≥ 5 cm below the costal margin, and exhibit platelet counts of $\geq 75 \times 10^9/L$ without the aid of transfusions.

In the CSR, patients will be reported in one of the following patient groups:

- Phase Ib group (All the Phase Ib escalation and expansion patients)
- Phase Ib expansion and Phase II stage 1 group (All the Phase Ib expansion and Phase II stage 1 patients)
- Phase Ib and Phase II stage 1 group (All the Phase Ib escalation, Phase Ib expansion and Phase II stage 1 patients)

according to the corresponding outputs and parameters analyzed.

2 Definitions and general methodology

